#### **4.2.2 *Presentation of treatment groups***

The following treatment group labels will be used in the tables, listings and figures, unless specified otherwise:

- ALX-0061 150 mg q2w + MTX (C201 PBO + MTX)
- ALX-0061 150 mg q2w + MTX (C201 75 mg q4w + MTX)
- ALX-0061 150 mg q2w + MTX (C201 150 mg q4w + MTX)
- ALX-0061 150 mg q2w + MTX (C201 150 mg q2w + MTX)
- ALX-0061 150 mg q2w + MTX (C201 225 mg q2w + MTX)
- ALX-0061 150 mg q2w + MTX (C201 all subjects)
- ALX-0061 150 mg q2w (C202 150 mg q4w)
- ALX-0061 150 mg q2w (C202 150 mg q2w)
- ALX-0061 150 mg q2w (C202 225 mg q2w)
- ALX-0061 150 mg q2w (C202 all subjects)
- All subjects

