## 7 SAFETY

### 7.1 Adverse Events

All safety summaries will be based on the safety population and presented by treatment group (see section 4.2.2). As study drug treatment is not interrupted between the parent study and this study, all adverse events reported in this study are considered treatment-emergent. However, unless specified otherwise, only adverse events that started after the first dose of C203 will be considered in the tables.

All adverse events will be coded and classified by System Organ Class (SOC) and Preferred Term (PT) using the medical dictionary for regulatory activity (MedDRA) that is current at the time of database lock.

A TEAE will be categorized as study drug-related if the relationship to study drug is reported to be 'possibly related' or 'related', or missing. In tabulations this categorization

will be used, but in the listings the original reported relationship will be presented. If the relationship is reported to be 'not applicable', it will not be considered in the tabulations.

A TEAE is reported as related to study procedure or not related to study procedure. Missing study procedure relationship will be considered as related.

A general summary table with AE events starting after first dose of C203 only will be produced to report the number and percentage of subjects with at least one event, the number of events and the incidence per 100 patient years, which will be calculated as:  $100 \times (\text{Number of subjects with AE}) / (\text{Total number of years observed while on C203, summed for all subjects})$ . Percentages will be calculated out of the number of subjects in the relevant treatment group.

The following categories will be included in the summary table:

- TEAE
- serious TEAE
- TEAE leading to death
- severe TEAE as classified by the investigator
- TEAE for which the study drug was interrupted
- TEAE for which the study drug was discontinued
- study drug-related TEAE
- serious study drug-related TEAE
- injection-site reaction.

Note that the TEAE here refers to the AEs starting after first dose of study drug in C203 study.

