A similar summary table will be produced for all TEAEs including those of the parent trials (C201 and C202). Any event happening either on parent trial or on the current trial will be considered for deriving the number and percentage of subjects with at least one event, and the number of events. The incidence per 100 patient years will be calculated as:  $100 \times (\text{Number of subjects with AE}) / (\text{Total number of years observed starting from the first dose in parent trial, summed for all subjects})$ .

Another summary table will be presented selecting adverse events of special interest. Search criteria for these adverse events can be found in section 16.5.

The following categories will be included in the summary table:

- infection
- serious infection (requiring hospitalization or i.v. antimicrobial treatment)
- opportunistic infection, excluding TB
- active TB infection
- latent TB infection
- Herpes zoster infection
- malignancy
- hypersensitivity reaction (including anaphylaxis and angioedema)
- hypersensitivity reaction (including anaphylaxis and angioedema) leading to withdrawal
- GI perforation
- demyelinating disorder
- MACE

This table will represent events which occurs only after the first dose of study drug in C203 study.

One more summary table for AEs of special interest will be produced including events from the parent trials as well. Any event happening either on parent trial or on the current trial will be considered for deriving the number and percentage of subjects with at least one event, and the number of events. The incidence per 100 patient years will be calculated as:  $100 \times (\text{Number of AEs}) / (\text{Total number of years observed starting from the first dose in parent trial, summed for all subjects})$ .

Tables by SOC and PT will report the number and percentage of subjects with at least one event, occurring only after the first dose of study drug on C203 study. Percentages will be calculated out of the number of subjects in the relevant treatment group.

These tables will be prepared for the following selections of AEs:

- TEAEs
- TEAEs by severity (Mild, Moderate, Severe)
- TEAEs with an incidence of at least 3%
- serious TEAEs
- non-serious TEAEs
- study drug-related TEAEs
- study procedure-related TEAEs
- TEAE for which the study or the study drug were discontinued

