### 13.4 Safety

**Table 14.3.1.1: Treatment-emergent adverse events: Summary table**

Summary table of TEAEs presenting the number of events, the number and percentage of subjects and the incidence per 100 patient years.

Population: safety population.

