**Table 14.3.1.3: Treatment-emergent adverse events: Incidence of adverse events of special interest**

Summary table of TEAEs of special interest presenting the number and percentage of subjects, the number of events and the incidence per 100 patient years.

Population: safety population.

**Table 14.3.1.4: Treatment-emergent adverse events: Incidence of adverse events of special interest including TEAEs from the parent trials**

Summary table of TEAEs of special interest including TEAEs from the parent trials presenting the number and percentage of subjects, the number of events and the incidence per 100 patient years.

Population: safety population.

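### SAP 7.1 puts a subject-based and an event-based rate under one incidence label, gives Table 14.3.1.3 no formula, and does not stop person-time at first event in the subject-based rate

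*SAP*

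**What the plan says.** SAP section 7.1 plans four summary tables with a rate per 100 patient years.

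- **Table 14.3.1.1** (all TEAEs, C203 only): the numerator is "Number of subjects with AE" and the denominator is "Total number of years observed while on C203, summed for all subjects".
- **Table 14.3.1.2** (all TEAEs, parent trials included): same numerator, over "Total number of years observed starting from the first dose in parent trial, summed for all subjects".
- **Table 14.3.1.4** (events of special interest, parent trials included): same denominator as Table 14.3.1.2, but the numerator becomes the number of AEs.
- **Table 14.3.1.3** (events of special interest, C203 only): section 7.1 lists the categories and gives the period, "This table will represent events which occurs only after the first dose of study drug in C203 study". It gives no rate formula.

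The index in SAP section 13.4 uses the same rate label throughout. The entry for Table 14.3.1.1 reads "Summary table of TEAEs presenting the number of events, the number and percentage of subjects and the incidence per 100 patient years", and the entry for Table 14.3.1.3 promises "TEAEs of special interest presenting the number and percentage of subjects, the number of events and the incidence per 100 patient years". SAP section 12.4.1 derives only AE onset day and duration, so it does not fill the gap.

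**The concern.** A reader meeting the same rate label in four neighbouring safety tables will take it to mean the same thing. It does not: two tables count people, one counts events, and one is undefined. Tables 14.3.1.3 and 14.3.1.4 have the same rows and will be read side by side, yet a programmer could copy the subject formula into the first from the other C203-only table, or the event formula from the other special-interest table.

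Separately, a subject counts at most once in the subject-based numerator but keeps adding time to the denominator after the first event. A person-time rate is meant to adjust for unequal follow-up, and for common events this one does not. Follow-up can differ here, because subjects may be withdrawn under the efficacy criteria at eight visits from Week 12 (Protocol 3.2.3.2) and the parent trials lasted 24 and 12 weeks. Long-term safety is half of the study objective.

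**Working it through.** The plan states no numerical rate, so there is no figure to reproduce.

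**Inputs.** Maximum follow-up in C203 is 114 weeks (Protocol 3.1.1). The parent trials lasted 24 weeks (C201) and 12 weeks (C202) (Protocol 3.2.1). Years = weeks × 7 / 365.25, so 24 weeks = 0.460, 114 = 2.185, 12 + 114 = 126 weeks = 2.415, and 24 + 114 = 138 weeks = 2.645.

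**Ceiling of the subject-based rate.** With N subjects, S of them with an event, the rate is 100 × S / (N × mean years). Since S ≤ N, it cannot exceed 100 / mean years. This needs no assumption about event rates.

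| Table and columns, full follow-up | Mean years | Ceiling |
|---|---|---|
| 14.3.1.1, all columns | 2.185 | 45.8 |
| 14.3.1.2, C202 columns | 2.415 | 41.4 |
| 14.3.1.2, C201 columns | 2.645 | 37.8 |

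The C202 ceiling in Table 14.3.1.2 is 138/126 = 1.095 times the C201 ceiling, only because that parent trial was 12 weeks shorter.

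Dropout also moves the ceiling. If 10%, 30% or 50% of subjects are observed for 24 weeks and the rest for 114 (assumed mixes), mean years are 2.012, 1.667 and 1.322, and the ceilings are 49.7, 60.0 and 75.6.

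**Dependence on follow-up below the ceiling.** With a constant event rate λ per year and common follow-up T, the expected subject-based rate is 100 × (1 − exp(−λT)) / T.

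- λ = 1 (assumed 100 per 100 patient-years, a very common row): 80.2 at 24 weeks, 40.6 at 114 weeks, 35.1 at 138 weeks.
- At 114 weeks, λ = 0.01, 0.05 and 0.10 give 0.99, 4.74 and 8.98, which are about 1%, 5% and 10% below the underlying rate.

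If time is stopped at the first event, expected time per subject is (1 − exp(−λT)) / λ. The ratio is then 100λ whatever the value of T.

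**Two readings of Table 14.3.1.3.** Take the infection row, 114 weeks for every subject and Poisson events (assumed).

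- Event rate 10 per 100 patient-years: prints 10.0 (events) or 9.0 (subjects).
- Event rate 40: prints 40.0 or 100 × (1 − exp(−0.40 × 2.185)) / 2.185 = 26.7, a ratio of 40/26.7 = 1.5.

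**Placebo time in the parent-inclusive tables.** With full follow-up, placebo time is 24/138 = 17% of the former-placebo column. Assuming equal arms (five C201 and three C202 groups in SAP 4.2.2; no arm sizes are given), it is 24/(5 × 138) = 3.5% of the pooled C201 column and 24/(5 × 138 + 3 × 126) = 2.2% of the grand total. If the placebo event rate is r times the on-drug rate and p is the placebo share, the event rate is multiplied by (1 − p) + p × r. For r from 0.5 to 1.25 (assumed) the factor is 0.91 to 1.04, 0.98 to 1.01 and 0.99 to 1.01 respectively.

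**The case against.** The strongest reply is that the subject-based formula is openly stated and the ceiling is a property of it, not an error. The analyses are descriptive, subject and event counts stand beside the rate, and no comparison between columns rests on it. The large distortions need very common events, and no document shows that follow-up will differ between columns. On this view two lines suffice: a formula for Table 14.3.1.3 and an events label for Table 14.3.1.4.

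Much of this stands. Those two lines would cure the labelling. They would not cure a person-time rate that falls with longer follow-up, and the unequal ceilings in Table 14.3.1.2 arise even with complete follow-up.

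A reader might infer more than the documents support:

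- *That all four tables are built differently.* Tables 14.3.1.1 and 14.3.1.2 share one construction over different stated periods.
- *That the general and special-interest tables contradict each other row by row.* They share no rows. A row-by-row mismatch can arise only between Tables 14.3.1.3 and 14.3.1.4.
- *That the information is lost.* In Tables 14.3.1.1 and 14.3.1.2 the event rate is the printed rate × events / subjects. All four tables use the safety population, so person-years can be worked back, to rounding. For C203 alone, first-event times can be derived from Listings 16.2.7.1 (AE start and onset day) and 16.2.1.4 (days to termination).
- *That placebo time materially distorts the pooled columns.* The factors above are within about 2% of 1, and the former-placebo column already names its origin.
- *That the end of observed time is a serious gap.* It most naturally means the last visit, in line with the AE window in Protocol 3.5.1. Stating it is a clarification.

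**Conclusion.** The point holds and should be fixed. One label covers two measures, and Table 14.3.1.3 can be programmed in two ways from the same plan. The subject-based rate is bounded by 100 / mean years observed and, for common rows such as any TEAE, falls as follow-up lengthens.

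The ceilings of 45.8, 41.4 and 37.8 follow from the stated durations and full follow-up alone. The 40.0 against 26.7 contrast rests on an assumed event rate of 40, Poisson events and 114 weeks for every subject.

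The effect is limited to reading and comparing printed rates. Rare rows such as death or malignancy barely change. This does not show that the plan hides harm: event counts, subject counts and percentages are untouched.

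**What to change.** In SAP sections 7.1 and 13.4, define two rates, label them separately, and apply both to Tables 14.3.1.1 to 14.3.1.4:

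1. *Subjects with first event per 100 PY* = 100 × subjects with an event / summed years to first event or end of observation.
2. *Events per 100 PY* = 100 × events / total years observed.

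State explicitly that both apply to Table 14.3.1.3. State that observation runs from the first dose in the table's period to the last visit, matching the AE collection window in Protocol 3.5.1. Add a rule for incomplete AE start dates in the time to first event, because SAP section 12.4.1 leaves onset day missing in that case.

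Optionally, footnote that the former-placebo, pooled C201 and grand-total columns of Tables 14.3.1.2 and 14.3.1.4 contain placebo-period events and time. A separate placebo display is not needed.

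The cost is one extra derivation and one extra rate per row. Onset time is already recorded in C203 (Protocol 3.5.1), but Tables 14.3.1.2 and 14.3.1.4 also need onset dates from the parent trials. The stated subject-based rates for common events will be higher than under the current formula.

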3.2.1. INCLUSION CRITERIA

Each potential subject must satisfy all of the following criteria to be enrolled in the study:

1. Must have been eligible for one of the preceding Phase IIb studies with ALX-0061 (ALX0061-C201 or ALX0061-C202), have been randomized to placebo or one of the ALX-0061 arms (subjects randomized to tocilizumab [TCZ] in Study ALX0061-C202 are not eligible) and completed the entire treatment and assessment period of the preceding studies (i.e., 24 weeks for Study ALX0061-C201 and 12 weeks for Study ALX0061-C202).
2. Must have reached at least 20% improvement in SJC and/or TJC at Week 24 for subjects participating in the preceding Phase IIb ALX0061-C201 study, or at Week 12 for subjects participating in the preceding Phase IIb ALX0061-C202 study.
3. Female subjects of childbearing potential (excluding postmenopausal women, sterilized, ovariectomized, and hysterectomized women) must agree to use 2 generally accepted adequate contraceptive methods of which 1 is a barrier method (e.g., hormonal contraception stabilized for at least 1 month [oral, patch, depot, injectable, vaginal ring] in combination with condom by partner) or should agree upon continuous abstinence from heterosexual contact from screening/baseline until at least 6 months after last dosing.
Male subjects must use condoms for the duration of the study and for at least 6 months after last administration of study drug.
4. Ability to comprehend and willingness to sign the informed consent form (ICF).
5. An understanding of and ability and willingness to adhere to the study visit schedule and other protocol requirements.

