3.2.2. EXCLUSION CRITERIA

Subjects meeting any of the following criteria may not be enrolled in the study:

1. Received TCZ during the preceding Study ALX0061-C202.
2. Received any prohibited treatment during the preceding Phase IIb studies (ALX0061-C201 or ALX0061-C202).
3. Diagnosis of or suspicion of a serious infection (requiring parenteral antibiotics and/or hospitalization) or TB during the preceding study.
4. Diagnosis of malignancy or demyelinating disease during the preceding study.

5. Any active or recurrent viral infection that based on the Investigator's clinical assessment make the subject unsuitable for the study, including recurrent/disseminated herpes zoster.
6. Diagnosis of congestive heart failure (CHF) class III or IV as defined by the New York Heart Association, unstable angina pectoris, myocardial infarction, cerebrovascular accident during the preceding study.
7. Planned donation of germ cells, blood, organs, or bone marrow during the course of the study or within 6 months thereafter.
8. Male with female partner who is planning to become pregnant within 6 months after last dosing.
9. Pregnant woman or female subjects who are breastfeeding.
10. History of anaphylactic reaction or serious hypersensitivity reaction during the previous study.
11. Anticipation that a live attenuated vaccine will be required during the study or within 6 months after last dosing.
12. Abnormality in laboratory test results observed at the Week 22 Visit for subjects participating in the preceding Phase IIb ALX0061-C201 study, or observed at the Week 10 Visit for subjects participating in the preceding Phase IIb ALX0061-C202 study:
 - a. ALT and/or AST levels \geq 2 times the ULN.
 - b. Hemoglobin levels \leq 85 g/L (8.5 g/dL).
 - c. Platelet count \leq $75 \times 10^9/L$ (75,000 cells/mm³).
 - d. Absolute neutrophil count: $< 1.5 \times 10^9/L$.
 - e. Serum creatinine levels \geq 1.5 mg/dL (133 μ mol/L).
 - f. Any other clinically significant abnormal laboratory result as evaluated by the Investigator.
 - g. If no laboratory test results of the Week 22 Visit (for subjects participating in the preceding ALX0061-C201 study) or the Week 10 Visit (for subjects participating in the preceding ALX0061 C202 study) are available, then laboratory values of tests performed between Week 22 and 24 (for study ALX0061-C201) or Week 10 and 12 (for study ALX0061-C202) will be taken into account for the exclusion criteria 12a to 12e listed above.

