### **Serious infections**

Any events like this will be listed under cluster = Infections, and can be identified based on AESER = Y

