**Malignancies**

Malignancies standardized MedDRA query (SMQ) (Narrow)

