**Demyelinating disorders**

Demyelination SMQ (Narrow)

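### Table 14.3.1.4 dilutes the malignancy and demyelination rates with parent-trial weeks that C203 entry selected to be event-free (9.5% or 17.4% low even at full follow-up), and the rate per 100 patient-years changes numerator between AE tables

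*SAP*

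**What the plan says.** SAP 7.1 plans four adverse-event summary tables, each with a rate per 100 patient-years. Tables 14.3.1.1 and 14.3.1.3 count events starting after the first C203 dose. Tables 14.3.1.2 and 14.3.1.4 add parent-trial events, and their denominator is "Total number of years observed starting from the first dose in parent trial, summed for all subjects". Table 14.3.1.4 uses the safety population (SAP 13.4) and has rows for serious infection, active TB, malignancy, demyelinating disorder, hypersensitivity and MACE, among others.

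Under Protocol 3.2.1, subjects must have "completed the entire treatment and assessment period of the preceding studies". Protocol 3.2.2 excludes:

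- no. 3: "Diagnosis of or suspicion of a serious infection (requiring parenteral antibiotics and/or hospitalization) or TB during the preceding study";
- no. 4: "Diagnosis of malignancy or demyelinating disease during the preceding study";
- no. 6: specified serious cardiac and cerebrovascular diagnoses in the parent trial;
- no. 10: anaphylactic or serious hypersensitivity reactions in the parent trial.

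SAP Appendix 5 selects malignancy and demyelination by narrow standardized queries (the latter by "Demyelination SMQ (Narrow"). Serious infections are any term in the Infections cluster that "can be identified based on AESER = Y", whereas SAP 7.1 describes the row as "serious infection (requiring hospitalization or i.v. antimicrobial treatment".

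The rate's numerator is subjects with an event in 14.3.1.1 and 14.3.1.2, and the number of events in 14.3.1.4. SAP 13.4 announces a rate for 14.3.1.3, but SAP 7.1 gives it no formula. SAP 11 (changes from the protocol analysis) mentions none of this.

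**The concern.** A subject reaches Table 14.3.1.4 only by having passed through the parent trial without the very events that several of its rows count. The parent weeks of these subjects are then time in which the event could not have occurred without removing the subject from the table. Counting that time lowers the rate in a known direction, and a larger sample does not cure it.

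Long-term safety is half of the study's only objective, there is no control arm, and this table carries the longest exposure. Its rates are likely to be read at face value.

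The changing numerator is a second, independent problem: tables with the same rate label cannot be compared, and the C203-only table that would reveal the dilution is the one without a formula.

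**Working it through.** **Inputs.** Parent time P = 24 weeks (C201) or 12 weeks (C202), Protocol 3.2.1. There is no gap: OLE Week 0 is the parent's Week 24 or Week 12 visit (Protocol 3.4.1.2). Maximum C203 follow-up: last dose at Week 102 plus 12 weeks = 114 weeks, which reproduces the figure in Protocol 3.1.1.

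**Formula.** Let the C203 event rate be constant, T the mean C203 follow-up in weeks, and f the parent-period rate among enrolled subjects as a fraction of the C203 rate. The printed rate is the C203 rate × (T + fP)/(T + P), so

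shortfall = P(1 − f)/(P + T).

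**Malignancy and demyelinating disorder (f = 0).**

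- T = 114: C201 24/138 = 17.4%; C202 12/126 = 9.5%. A true 1.00 per 100 patient-years prints as 0.826 or 0.905.
- All subjects, T = 114: 18/132 = 13.6% if C201 supplies half, 21/135 = 15.6% if it supplies three quarters. With eight equal groups (five C201, three C202) it is 156/1068 = 14.6%. These shares are assumptions.
- Efficacy stop at Week 48: last dose Week 46, follow-up Week 58, so T = 58: C201 24/82 = 29.3%; C202 12/70 = 17.1%.
- Efficacy stop at Week 12: last dose Week 10, T = 22: C201 24/46 = 52.2%; C202 12/34 = 35.3%.

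Since 114 weeks is the maximum, 17.4% and 9.5% are the smallest shortfalls over follow-up lengths when f = 0.

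**Serious infection and active TB (f above 0).** The seriousness flag in Appendix 5 is wider than exclusion 3, because an infection can be serious without hospitalization or parenteral antibiotics. The TB term list includes erythema induratum and exposure to communicable disease, which need not be TB. Some parent events can therefore count. With f = 0.10 (assumed) at 114 weeks: 21.6/138 = 15.7% and 10.8/126 = 8.6%. With f = 0.25 (assumed): 18/138 = 13.0% and 9/126 = 7.1%.

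**MACE and hypersensitivity.** Exclusions 6 and 10 remove part of what the Appendix 5 queries capture. The direction is the same; the documents do not allow a size.

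**Against sampling error.** Assume 501 subjects followed 114 weeks: 501 × 114/52.18 = 1095 patient-years. The pooled shift divided by the Poisson standard error of the C203 rate is 0.146 × √events:

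| Assumed rate per 100 PY | Expected events | Shift / SE |
|---|---|---|
| 0.1 | 1.1 | 0.15 |
| 0.5 | 5.5 | 0.34 |
| 3.0 | 32.8 | 0.84 |

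At 3.0, if everyone were followed only 58 weeks, the shortfall would be 19.5/77.5 = 25.2% with 16.7 events, a ratio of 1.03. Fewer subjects reduce the ratio.

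**Numerator.** Tables 14.3.1.2 and 14.3.1.4 share population and denominator. Infection (events) prints above any TEAE (subjects) once mean infections per subject exceed the proportion with any TEAE. For illustration, assume 80% with a TEAE, 1.0 infection per subject and 133.5 weeks (2.558 years) each: 80/2.558 = 31.3 against 100/2.558 = 39.1. For one event type with Poisson counts over 138 weeks, subjects per year is 0.97 of events per year at a rate of 2 per 100, 0.88 at 10 and 0.69 at 30. The switch matters little for rare events and considerably for common ones.

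**The case against.** The best defence is that Table 14.3.1.3 already reports the same categories for C203-onset events, and that 14.3.1.4 is its deliberate companion. Different start dates for person-time in the two pairs of tables are intended and are not an error. The study is descriptive, the safety endpoints in SAP 3.3 are counts and percentages, and both subjects and events are printed, so a determined reader can often recompute a crude rate. Against noise the shift is small: a single C201 column with an eighth of 501 subjects, at an assumed 3.0 per 100 patient-years, gives about 4.1 events and a shift of 0.174 × √4.1 = 0.35 standard errors.

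All of this limits the impact and stands. It does not remove the fault. Without a formula, 14.3.1.3 cannot be assumed comparable with 14.3.1.4, and nothing in the plan warns the reader that entry selection emptied the parent weeks.

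A reader might infer that all four rows are event-free in the parent period. The documents do not support that. Only malignancy and demyelinating disorder come close, and even there the terms behind the queries are not listed, so mapping differences and protocol deviations could let an occasional event in.

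**Conclusion.** The point holds as a modest, one-directional reporting bias in a supplementary table, plus a rate that is not one quantity across four tables. For malignancy and demyelinating disorder, SAP 7.1 as written gives rates low by 17.4% (C201) or 9.5% (C202) at 114 weeks, assuming a constant rate and no parent events, and by more with shorter follow-up. Serious infection and active TB are low by a smaller, unknown amount; MACE and hypersensitivity are partly affected.

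Two stronger readings should be resisted. First, 17.4% is not a worst case: it is an upper limit only with respect to parent events, and a lower limit with respect to follow-up length. Second, this is not a failure of the safety analysis. The C203-only tables carry no parent time, and the shift is probably below one standard error, although that comparison and the 31.3 versus 39.1 illustration rest on assumed rates and follow-up.

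**What to change.** (a) In Table 14.3.1.4, for malignancy, demyelinating disorder, serious infection and active TB, base the rate on C203-onset events and C203 person-time, so that it equals the rate in 14.3.1.3. Show any parent-onset events beside it as a count so that none is lost, and footnote the entry selection. Footnote MACE and hypersensitivity as partly selected.

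(b) State one rule for the rate per 100 patient-years and use it in all four tables: the same numerator, the start of person-time named for each table, and its end at the last visit, which matches the TEAE recording window in Protocol 3.5.1. Write the rule out for 14.3.1.3.

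The cost is SAP wording and minor programming, with no new data. The affected rates become slightly less favourable, and a few rows of 14.3.1.4 carry a different, footnoted denominator.
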